14.7 WEEK 12, 24,36, 48 and WEEK 80 FOLLOW-UP STUDY VISITS

These visits will be conducted in clinic, face to face at 24 and 80 weeks post randomisation. The following data will be collected.

- Steroid and DMARD use
- (S)AE reporting (including Adverse Events related to glucocorticoid toxicity e.g. infection, diabetes, hypertension and fracture)
- Relevant medical history
- Urea & Electrolytes (U&E) test
- Full blood count
- Liver function test
- PMR Activity Score (52), requiring: (week 24 & 80 only)
 - CRP;
 - Physician VAS assessing disease activity;
 - Number of minutes of morning stiffness;
 - Upper limb elevation / active shoulder abduction; (EUL) graded as 0-3
 - Participant pain VAS (0-10) (see section 14.10)
- Weight
- Hip and waist circumference (week 80 only)
- HbA1C test(week 24 & 80 only)

- ESR test
- Physical examination – MSK system including elevation of upper limbs, joint swelling/tenderness/limitation of movement, and vascular including temporal arteries
- Vital Signs – including, BP, heart rate, temperature
- Participant questionnaires (see section 14.10)

14.8 SCREENING FOR POSSIBLE ADRENAL INSUFFICIENCY

At the point that the participants steroid dose drops below 5mg of prednisolone or equivalent for the first time during the trial period, a 9am cortisol test is suggested. Because of the requirement for a 9am blood test, it is likely that participants will prefer to have this done at their local pathology clinic, rather than necessitating a separate hospital visit.

In relation to this test, the data listed below will be collected.

- 9am cortisol test result
- Confirmation of current steroid dose at the time the cortisol test was done.
- Statement that result has been reviewed, and whether participant is judged to be at high, moderate or low risk of adrenal insufficiency; and whether steroid dosing advice has changed in response to this, further testing arranged including repeat 9am cortisol and/or synacthen test, steroid sick day rules provided, and/or discussion with or referral to Endocrinology

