5.3 THE NEED FOR BETTER TREATMENT OPTIONS FOR PMR

Glucocorticoid (“steroid”) therapy rapidly brings the pain and stiffness of PMR under control, with a corresponding improvement in physical and mental health-related quality of life compared to untreated PMR (14). However, steroid therapy has multiple unwanted effects (steroid toxicity), which accumulate over time and may not be fully reversible even after the steroid treatment has stopped (15). Older patients such as those with PMR are particularly susceptible to steroid toxicity. Patients whose duration of prednisolone therapy has been prolonged by dose-escalations related to PMR relapses are likely to be at the greatest risk of long-term steroid toxicity.

Steroid treatment for PMR confers a 63% increased risk of fracture (16), at least a twofold increased risk of diabetes(17) and a dose-dependent increased risk of infection (18). The risk of infection is related to both current and cumulative dose. Prolonged steroid therapy (daily dose of 5mg prednisolone-equivalent or greater, for 4 weeks or more) can cause adrenal insufficiency that may persist for months to a year or more after the steroid dose is tapered below 5mg daily (19)

Other outcomes of glucocorticoid therapy listed in the Outcome Measures in Rheumatology Clinical Trials (OMERACT)-endorsed Core Domain Set for adverse impacts of glucocorticoid therapy include weight gain, mood disturbance, and fatigue (20). 15% of patients with PMR are reported to experience depression (21) which is likely to represent the combined effect of the disease and the treatment.

An adjunctive treatment that could reduce steroid requirements in relapsing PMR would have the potential to substantially improve long-term physical and mental health of this patient group.

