6.3 SECONDARY OBJECTIVES

Secondary objectives are:

- to assess the impacts over 18 months of adding DMARD to steroids, by comparing treatment groups for:
 - PMR symptom severity (PMR-IS and sub-domains)
 - Health-related quality of life (EQ-5D-5L)
 - PMR Disease Activity (PMR-AS)
 - time to steroid cessation
 - steroid-free remission at 18 months
 - time to PMR relapse and number of PMR relapses
 - cumulative (prednisolone equivalent) steroid dose prescribed

- Safety:
 - adverse events of special interest related to investigational medicinal products or PMR
 - serious adverse events and SUSARs
 - glucocorticoid toxicity
 - diagnosis of adrenal insufficiency
 - time to diagnosis of GCA
- to estimate cost-effectiveness over 18 months post randomisation via a within-trial analysis and the long-term impact of the treatment options using a decision analytical model.
- to estimate the impact of adoption of the intervention on rheumatology service capacity

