14 ASSESSMENTS/SAMPLES/DATA COLLECTION

14.1 SUBMISSION OF TRIAL DATA

Informed Consent Documents, Serious Adverse Events (SAE), Suspected Unexpected Serious Adverse Reaction (SUSAR) and Participant Questionnaire Booklets will be collected via paper case report forms. CTRU will provide an electronic copy of these forms to be printed and completed by research staff at site and the information sent to CTRU, usually by electronic secure file transfer. All other data collection will be via Remote Data Entry (RDE) on electronic case report forms (eCRFs) managed by the CTRU at the University of Leeds. Access to the live STERLING database will be provided by the CTRU following sites being authorised to open to recruitment; guidance on RDE and completing eCRFs will be provided.

Data must only be completed by personnel authorised to do so by the Principal Investigator, as recorded on the trial-specific Authorised Personnel Log.

Where additional documentation is required by CTRU, for example hospital reports and letters, it is the responsibility of staff at research sites to redact all personal identifiable data prior to sending to CTRU. Such records should only include trial number, initials and date of birth to identify the participant. The exception to this is the participant consent form, where the participant's name and signature must not be redacted.

Participating hospitals will be expected to maintain a file of essential trial documentation (Investigator Site File) that will be provided by CTRU, and where applicable, keep copies of all sites completed paper CRFs for the trial (with the exception of QoL & Healthcare Resource use questionnaires).

14.2 SCHEDULE OF EVENTS.

Not included in this table: on reaching below 5mg prednisolone or equivalent for the first time, a 9am cortisol blood test should be performed (sections 14.6 & 14.8).

Participant Consent	Follow-up schedule (weeks);							Telephone Contact (Weeks)	DMARD monitoring blood tests	Blood Pressure (LEF only)
	Screening	Baseline (0)	12	24	36	48	80	4, 8, , 60, 72	As per local guidelines ††	As per local guidelines ††
Target Visit Window	Max. 6 weeks between Screening and Baseline		-/+ 2 weeks	-/+ 2 weeks	-/+ 2 weeks	-/+ 2 weeks	-/+ 2 weeks			
Written Informed Consent/Witnessed verbal informed consent	x									
Reg and Rand										
Registration	x									
Randomisation		x								
Trial Assessments			12	24	36	48	80			
Eligibility Checks	x	x								
Steroid Use Review		x	x	x	x	x	x	x		

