The current steroid dose being taken by the participant, and the participant's current rate of steroid taper, will be used to determine whether the dose is likely to fall below 5mg prednisolone equivalent before the next scheduled study contact. If so, the participant will be advised of the need for a 9am cortisol blood test to screen for possible adrenal insufficiency. This test will be requested in advance by the site study team and the participant will be advised when they will need to have this test done, and

appropriate advice as to how it should be taken (blood to be drawn at 9am at least 24 hours after the most recent steroid dose).

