As for the primary outcome, if any steroid medications other than prednisolone are prescribed, these will be converted to an agreed “prednisolone equivalent dose” prior to analysis.

Safety

Adverse events (AEs) of Special Interest reported over 18 months post randomisation will include those relevant to PMR and/or investigational medicinal product.

Serious adverse events (SAEs) and SUSARs regardless of relationship to PMR or investigational product reported over 18 months post randomisation.

Glucocorticoid toxicity

Glucocorticoid toxicity is defined as per the OMERACT Glucocorticoid Core Domain Set (infection, diabetes, hypertension, fracture) adapting measures from the Glucocorticoid Toxicity Index (67)

Time to development of GCA

Time to development of GCA (defined as rheumatologist-confirmed and treated according to GCA treatment protocols specified in 2020 BSR guideline, without the diagnosis later being revised from GCA during the 18 month period) will be defined as the duration between randomisation and date of GCA diagnosis. Participants who are not diagnosed with GCA during follow-up will be censored at 18 month, or else at date of death or withdrawal.

Proportion of participants diagnosed with adrenal insufficiency

The proportion of participants who are identified as diagnosed with adrenal insufficiency will be the proportion of participants who either have a low value of 9am cortisol test, or an intermediate value followed by a positive short synacthen test, at any point during follow-up. Adrenal insufficiency screening tests (9am cortisol) will be conducted within the trial but confirmation of physician diagnosis of adrenal insufficiency, will be recorded, along with the relevant date and actions taken in response.

Deaths

Deaths from all causes over 18 months post randomisation. Date of death will be recorded, and time to death will be derived as days from randomisation to death.

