Time to development of GCA will be summarised using Kaplan-Meier estimates. Adjusted hazard ratios will be estimated using Cox proportional hazards regression or parametric alternative, with covariates for minimisation factors (fitting centre as a random effect, if feasible) age and treatment group, and reported with 95% CI.

Adrenal insufficiency: The proportion of participants considered to be experiencing adrenal insufficiency will be reported in both groups.

Deaths: Number of deaths from all causes over 18 months post randomisation and time to death will be summarised by treatment received

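### Cortisol screening is triggered by first falling below 5mg, which the DMARD is meant to make more common, but adrenal insufficiency is reported per arm without regard to who was tested

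*Protocol*

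**What the plan says.** Three places in the protocol govern when the cortisol test happens. Section 14.8 sets the trigger, "At the point that the participants steroid dose drops below 5mg of prednisolone or equivalent for the first time during the trial period", and describes the test as a suggestion. The note to the schedule of events in section 14.2 uses the same threshold in firmer terms: "on reaching below 5mg prednisolone or equivalent for the first time, a 9am cortisol blood test should be performed". Section 14.6 has the site use the current dose and rate of taper to judge "whether the dose is likely to fall below 5mg prednisolone equivalent before the next scheduled study contact", and the test is advised only if so. The visit table in 14.2 has no cortisol row, and cortisol is not among the assessments listed in 14.7 for weeks 12 to 80.

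Section 16.2.2 defines the outcome as "the proportion of participants who either have a low value of 9am cortisol test, or an intermediate value followed by a positive short synacthen test", counted over the whole of follow-up. Section 18.3 gives the analysis: "The proportion of participants considered to be experiencing adrenal insufficiency will be reported in both groups". Neither section restricts the denominator to those tested or gives untested participants a category of their own.

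The item "diagnosis of adrenal insufficiency" is listed under safety in the secondary objectives (6.3). Section 5.3 says that 5mg or more daily for at least 4 weeks "can cause adrenal insufficiency that may persist for months to a year or more" after the dose goes below 5mg.

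**The concern.** Whether a participant has the protocol-driven test depends on a dose reached after randomisation. The treatment hypothesis (5.6) is that the DMARD reduces flares during the taper and so reduces steroid exposure, and the design targets a 30% reduction in cumulative dose (section 17). If the DMARD works, more of that arm should pass below 5mg and be tested.

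A participant who stays at or above 5mg has no scheduled test and cannot enter the numerator through screening. By the account in 5.3, these participants have had the exposure that can lead to adrenal insufficiency. A per-group proportion of all participants therefore reflects two things that cannot be separated: how many were tested, and how many of those tested were positive.

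At stake is the reading of one glucocorticoid harm. A higher proportion in the DMARD arm could come from more testing alone, and a true benefit could be hidden.

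There are two smaller wording problems. Sections 14.2 and 14.8 differ on how firmly the test is required, and in an open-label trial uptake of an optional test may differ by arm. Inclusion criterion 4 also sets no minimum dose, so it is unclear how the trigger applies to someone who enters already below 5mg.

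**Working it through.** **Inputs from the protocol (section 17).** Control mean cumulative dose 5g over 18 months, coefficient of variation (CV) 0.78, log-normal distribution, target reduction 30%, two-sided 5% significance, 20% attrition, 200 participants, 1:1 allocation. The protocol gives no figure for adrenal insufficiency, for the share of participants falling below 5mg, or for positivity on testing. The last two are assumptions below.

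**Step 1: reproduce the design figure, to confirm the dose model.**
- SD on the log scale = √ln(1 + 0.78²) = 0.689; effect = |ln 0.7| = 0.357.
- The noncentral-t calculation gives 80 per arm (power 90.2%), so 160 evaluable, and 160 / 0.80 = 200.
- At CV 0.94 the power with 80 per arm is 80.4%.
- Both stated figures reproduce.

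**Step 2: the identity.** Through screening,

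reported proportion = P(tested) × P(positive given tested).

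If positivity is equal in the two arms, the ratio of reported proportions equals the ratio of tested shares, whatever the positivity. The artefact cancels only if the risk ratio among those tested (DMARD to control) equals control tested share / DMARD tested share.

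**Step 3: assumed tested shares, equal positivity.**

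| Tested, control v DMARD | Reported at 20% positive | Reported at 40% positive | Apparent ratio | Risk ratio that cancels it |
|---|---|---|---|---|
| 40% v 50% | 8% v 10% | 16% v 20% | 1.25 | 0.80 |
| 50% v 70% | 10% v 14% | 20% v 28% | 1.40 | 0.71 |
| 40% v 60% | 8% v 12% | 16% v 24% | 1.50 | 0.67 |

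**Step 4: tested shares suggested by the protocol's own dose model.**
- Taking 18 months as 546 days, the mean daily dose is 5000/546 = 9.16mg in control and 3500/546 = 6.41mg on DMARD.
- Log-scale mean, control = ln 9.16 − 0.689²/2 = 1.977.
- Control share averaging below 5mg = Φ((ln 5 − 1.977)/0.689) = Φ(−0.53) = 29.7%.
- DMARD share = Φ((ln 5 − 1.977 + 0.357)/0.689) = Φ(−0.02) = 49.4%.
- Ratio = 1.66; with 560 days (80 weeks) it is 1.64. The risk ratio that cancels it is 0.297/0.494 = 0.60.
- Reported proportions at equal positivity: 5.9% v 9.9% (20% positive) and 11.9% v 19.7% (40% positive).

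Anyone whose average is below 5mg was below 5mg at some time, so each share is a lower bound on the share ever below 5mg. It is not an estimate of the share tested: it includes people already below 5mg at entry and assumes full uptake. The true ratio may differ from 1.65.

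**Step 5: can a real benefit be reversed?** Take tested shares of 40% v 60% and positivity of 20% in control and 15% on DMARD, a true risk ratio among those tested of 0.75. The reported proportions are 0.40 × 0.20 = 8% and 0.60 × 0.15 = 9%. The table then points against the DMARD although risk among those tested is lower on it. Reversal occurs here because 0.75 is above the cancelling value of 0.67.

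**The case against.** The strongest reply has four parts.

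- **The direction is not fixed.** The DMARD arm shows more cases only if risk among those tested is not much lower there. Lower cumulative exposure could reduce it, and below the cancelling ratio (about 0.60 to 0.80 in these scenarios) the table would favour the DMARD. This stands. A reader might infer that a DMARD that works must show more adrenal insufficiency; the protocol does not support that without the equal-positivity assumption.
- **Part of any excess may be real.** Section 15.2.1 lists diagnosis of adrenal insufficiency among the expected events of tapering. More cases in an arm that tapers further could be a genuine consequence of the strategy. This also stands, and it is why the testing component needs to be shown separately.
- **Detection is not confined to the screen.** A diagnosis is a reportable adverse event in either arm (15.2.1), and section 16.2.2 records physician confirmation. This limits the bias, but the defined outcome rests on test results.
- **The analysis plan could settle the denominator.** Section 18.1 leaves analysis populations to it, and no sentence in the protocol says that untested participants count as negative. A reader might infer such a rule; it is only the effect of following the stated definition literally. The protocol does, however, itself fix the trigger, the definition and the reported statistic, and the problem lies in their combination.

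The gap for participants entering below 5mg is set before randomisation, so it should balance between arms. It is a wording gap, not a source of bias.

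**Conclusion.** The concern holds in this limited form. The comparison of adrenal insufficiency between arms is confounded by who was tested, because the test depends on a post-randomisation event that treatment is intended to affect. At equal positivity the apparent ratio against the DMARD arm equals the ratio of tested shares. The range of 1.25 to 1.65 rests on assumed shares and, at its upper end, on the protocol's log-normal dose model with average dose standing in for the trigger.

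The consequence is bounded. Section 18.3 plans no test, ratio or confidence interval for this outcome, and neither the primary analysis nor any error rate is affected. A reader might also infer that prolonged steroid use in the control arm would be made to look safe overall. That goes too far, because infection, diabetes, hypertension and fracture are reported separately as glucocorticoid toxicity. What remains is one safety table that could mislead, and it is worth correcting before the data are tabulated.

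**What to change.** In 16.2.2 and 18.3, replace the single proportion with counts by arm: already below 5mg at randomisation, first reaching below 5mg during the trial, tested, and positive. Show participants without a test as not assessed. Label the proportion positive among those tested as descriptive only, since it conditions on an event that treatment affects and so is not a clean randomised comparison either. State that the proportion of all randomised participants is not to be read on its own as a difference in harm between arms.

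Reconcile sections 14.2 and 14.8 on the status of the test, and make clear how they apply to participants who enter below 5mg. Which clinical rule to adopt is for the investigators.

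The cost is wording and a few table rows. The reporting change needs no added tests: baseline steroid use, the cortisol result and the dose at testing are already collected (14.5, 14.8), and the steroid questionnaire runs every four weeks (14.10).

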14.9 DMARD MONITORING

Participants allocated to MTX and LEF must also undergo the following procedures and information collection in line with local practice in order to determine the safety of these IMPs and to establish if it is safe to continue with the treatment.

As a guide the British Society for Rheumatology DMARD monitoring guidelines recommend FBC, U+E and LFT:

- every two weeks until on stable dose for six weeks
- then monthly for three months
- quarterly thereafter

This data will not be recorded on the CRFs unless it qualifies as an Adverse Event. Please refer to the corresponding schedule of events table for the time points (Section 14.2):

The site team will issue sufficient laboratory request forms to cover the duration of each prescription and will check the results of the monitoring blood tests before each new prescription of MTX is issued.

Subject to agreement of the GP practice, the participant may have the blood draws taken at their GP practice, providing the results can be accessed by the team.

Providing the results of the prior test do not fall outside the limits referred to in section 13.4.1 (and are acceptable according to local physician discretion windows either side of the scheduled blood monitoring dates will be allowed. Please see Schedule of Events for details of appropriate windows.

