7.4.3 DMARD monitoring blood tests (if taking DMARD)

Participants receiving DMARD therapy will require DMARD monitoring blood tests according to local guidelines. The British Society for Rheumatology guideline for DMARD monitoring suggests full blood count and liver function tests every 2 weeks until on stable DMARD dose for 6 weeks, followed by monthly for 3 months, and then quarterly (every 3 months) thereafter (32).

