13.1.2 Ongoing Blood monitoring during methotrexate therapy

Blood monitoring of methotrexate will follow local recommendations. As a guide the British Society for Rheumatology DMARD monitoring guidelines recommend FBC, U+E and LFT approximately 8ml taken each draw:

- every two weeks until on stable dose for six weeks
- then monthly for three months and
- quarterly thereafter

The site team will issue sufficient laboratory request forms to cover the duration of each prescription and will check the results of the monitoring blood tests before each new prescription of MTX is issued. Providing the results of the prior test do not fall within the limits referred to in section 13.4.1 and are acceptable according to local physician discretion, windows either side of these blood monitoring dates will be allowed. Please see Schedule of Events for details of appropriate windows.

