13.1.11 Methotrexate Target Dose

The earliest timepoint for potential dose escalation will be following the week 4 telephone assessment, but may occur following any of the telephone assessments up to the week 26 clinical assessment.

Dose escalation should only be performed once the latest DMARD monitoring blood tests (see section 13.1.2) have been checked to assess for any biochemical/haematological abnormalities (see section 13.4.1) and where the participant is not experiencing other intolerable toxicities e.g. nausea.

If DMARD monitoring is satisfactory (see section 13.4.1), participants should be advised to increase their MTX dose in line with their Target Dose. The Target Dose is 25mg weekly for most participants, but prescribers should consider reducing the Target Dose to 20mg weekly for participants with renal dysfunction or frailty.

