13.3.4 Ongoing Blood monitoring and Blood therapy

Pressure Assessments during Leflunomide

Monitoring of leflunomide via blood tests and blood pressure measurements will follow local recommendations. As a guide the British Society for Rheumatology DMARD monitoring guidelines recommend FBC, U+E, LFT and a blood pressure measurement:

- every two weeks until on stable dose for six weeks
- monthly for three months and
- quarterly thereafter

Blood Tests

The site team will issue sufficient laboratory request forms to cover the duration of each prescription and will check the results of the monitoring blood tests before each new prescription of LEF is issued.

Providing the results of the prior tests do not fall within the limits referred to in section 13.4.1 and are acceptable according to local physician discretion, windows either side of these blood monitoring dates will be allowed. Please see Schedule of Events for details of appropriate windows.

Blood Pressure

Blood pressure (BP) should be measured at the same time as each blood test. Participants who transfer onto LEF from MTX will be issued with their own blood pressure monitor. Therefore, it is acceptable for the BP to be measured either by the GP practice or self-managed by the participant. Participants will receive instruction from the research team regarding the use of the monitor and written instructions advising them that:

- should the BP value be over 140/90 then it should be rechecked on another occasion within one week. If on re-checking, it is still over 140/90, then the site research team should be notified within one further week.
- should the BP value be over 180/120 (regarded as severe hypertension), the research team should be contacted on the next working day so that appropriate clinical action can be taken.

The team will promptly communicate new or significant findings of high blood pressure to the GP, as this may require escalation of antihypertensive therapy by the GP.

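### DMARD monitoring adds about 10 to 21 blood tests to the 5 common to both arms, and its results are recorded only as adverse events, so laboratory event counts partly reflect testing intensity

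*Protocol*

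**What the plan says.** Sections 14.2 and 14.7 give both arms U&E, FBC, LFT and vital signs (including blood pressure) at weeks 12, 24, 36, 48 and 80.

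On top of this, 7.4.3 states "Participants receiving DMARD therapy will require DMARD monitoring blood tests according to local guidelines". The guide schedule in 13.1.2 and 14.9 is "every two weeks until on stable dose for six weeks", "then monthly for three months", and "quarterly thereafter". Section 13.1.11 allows methotrexate escalation from week 4 and says it "may occur following any of the telephone assessments up to the week 26 clinical assessment", which can lengthen the two-weekly phase. On what is kept from these tests, 14.9 says "This data will not be recorded on the CRFs unless it qualifies as an Adverse Event".

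For leflunomide, 13.3.4 ties a blood pressure measurement to each blood test and adds: "Participants who transfer onto LEF from MTX will be issued with their own blood pressure monitor". Section 16.2.2 then says: "Glucocorticoid toxicity is defined as per the OMERACT Glucocorticoid Core Domain Set (infection, diabetes, hypertension, fracture").

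Section 18.3 reports adverse events of special interest by treatment received (MTX, LEF, both or neither) and by severity. Nothing in 14.9 or 18.3 allows for the difference in testing frequency or asks how an event was found.

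**The concern.** An abnormality that comes and goes is more likely to be caught in someone tested often. The monitoring tests contribute to the CRF only when they yield an event, so the normal results, and the number of tests behind them, are not captured from that source. The reader of a table with columns MTX, LEF, both and neither will compare the columns, and the neither column is the least tested.

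The trial is meant to weigh DMARD adverse effects against reduced steroid toxicity (section 5.4). If part of the excess of deranged LFT or cytopenia on DMARD comes from more frequent testing, the trade-off is blurred in the direction unfavourable to the DMARD. Hypertension needs separate care because it is both an expected leflunomide effect (15.2.3) and part of the glucocorticoid toxicity outcome, where extra detection could offset a real steroid-sparing benefit.

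**Working it through.** The protocol gives no figure for testing intensity, so there is none to reproduce. The counts below follow from its guide schedule.

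**Inputs.** Two-weekly tests until six weeks after the last dose change, three monthly tests, then quarterly tests to week 80 (13.1.2, 14.9). Last dose change between week 0 (none) and week 26 (13.1.11). Five post-baseline tests common to both arms (14.2, 14.7). I take a month as 52/12 weeks and a quarter as 13 weeks.

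**Formula.** With the last dose change at week c:
- two-weekly tests = (c + 6)/2
- monthly tests = 3, spanning 13 weeks
- quarterly tests = whole part of (80 − (c + 6) − 13)/13

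| Last dose change | Two-weekly | Monthly | Quarterly | Monitoring tests | Ratio to 5 |
|---|---|---|---|---|---|
| none | 3 | 3 | 4 | 10 | 2.0 |
| week 4 | 5 | 3 | 4 | 12 | 2.4 |
| week 8 | 7 | 3 | 4 | 14 | 2.8 |
| week 12 | 9 | 3 | 3 | 15 | 3.0 |
| week 26 | 16 | 3 | 2 | 21 | 4.2 |

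The last row is an upper figure, because it takes two-weekly testing as unbroken to week 32.

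**All tests in a DMARD participant.** If a monitoring test within two weeks of a scheduled visit replaces that visit's test, the totals for the five rows are 14, 13, 16, 18 and 23, or 2.6 to 4.6 times the common five. If none are merged, they are 15, 17, 19, 20 and 26, or 3.0 to 5.2 times.

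**Dependence on the visit schedule.** Section 7.4.1 puts in-person follow-up at weeks 24 and 80 only, with telephone contact at weeks 12, 36 and 48. If only those two visits produced common bloods, monitoring alone would be 10/2 = 5 to 21/2 = 10.5 times the common tests. The comparator count therefore depends on a point the protocol leaves inconsistent.

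**Blood pressure.** Both arms have it measured at study visits (14.7). After a switch to leflunomide, it is also measured with each monitoring test. A reading over 140/90 that persists on recheck goes to the site, and significant findings go on to the GP, who may escalate treatment (13.3.4). New or increased antihypertensive medication is how 15.2.3 defines the hypertension event. The extra readings can thus lead to a recorded event, but only in those who switch.

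**The case against.** **Descriptive tables and an unseen SAP.** Section 18.3 plans no test or effect estimate for these events, and which visits feed a safety table is commonly left to the SAP. That is fair, and it keeps the point modest. But the recording rule in 14.9 is fixed in the protocol, and unless the CRF captures how an event was detected, later analysis cannot recover it from that source.

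**Reporting filters.** Sections 15.2.2 and 15.2.3 require CTCAE grade 2 or above and, for LFT and cytopenia, clinical significance in the local investigator's judgement. Persistent abnormalities would be found at the common visits anyway. This stands. A reader might infer that event counts will be inflated two- to fourfold because the tests are. That would require independent, transient, reportable abnormalities at the same rate per test in both arms, and the protocol gives no such rate.

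**Hypertension.** A reader might infer over-detection across the whole DMARD arm. Monitors go only to those who switch to leflunomide, a medication change is needed for the event, and 18.3 already separates those columns. Section 16.2.2 does not say whether home readings count towards glucocorticoid toxicity, so that route is possible rather than established.

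**Common visits only.** It is tempting to replace the tabulation with common-visit results. That would be worse: it omits everything before week 12, when methotrexate is started and first escalated. It would also lose abnormalities found at monitoring, acted on under 13.4.1, and resolved by the next visit. The error would then favour the DMARD.

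**Part of the strategy.** Monitoring belongs to the strategy being tested, so what it finds is a real consequence of that strategy. This is a good reason to keep the full tabulation, but it does not make raw counts a clean comparison of drug effect.

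**Conclusion.** The point holds as a low-cost improvement to safety reporting. On the guide schedule, DMARD participants have about 10 to 21 monitoring tests by week 80 in addition to the 5 scheduled in both arms. Counts of deranged LFT and cytopenia by treatment received will therefore partly reflect testing intensity. The effect on event counts cannot be sized from the protocol and is reduced by the reporting filters. For hypertension, the concern is confined to participants who switch to leflunomide, and is a possibility only.

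The test counts assume that sites follow the guide, that participants stay on a DMARD to week 80, and that the five visits of 14.2 and 14.7 take place. The primary outcome is not affected, and the monitoring itself need not change.

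**What to change.** 1. Keep the full tabulation of all adverse events in 18.3 as it is.
2. Add to 18.3 a supplementary comparison, by randomised arm, of LFT and blood-count abnormalities and of blood pressure, using only results from the scheduled visits common to both arms. State that it supplements the full tabulation and does not replace it.
3. Add a CRF field for how each laboratory or hypertension event was detected: scheduled visit, DMARD monitoring, home blood pressure, or other. Show events found only at monitoring or by home readings on a separate line.
4. Reconcile the in-person visits in 7.4.1 with those in 14.2 and 14.7, since they determine which results are common to both arms.

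The cost is one CRF field and one table; 14.2 and 14.7 already plan the scheduled-visit measurements in both arms. The limitation is that the common-visit comparison misses abnormalities that arise and resolve between visits, so it should always be read beside the full tabulation.
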